Title: Effect of Soluble Corn Fiber Supplementation for 1 Year on Bone Metabolism in Adolescents

NCT Number: NCT02916862

Date of the document: 09/26/2025

STUDY DESIGN AND METHODS

Study rationale and overall design

The MetA-Bone trial was a double-blinded placebo controlled clinical trial to determine the effects of SCF supplementation for one year on bone mass in children and adolescents. Details of the trial were published elsewhere (25). Briefly, the primary outcome was change in total and spine BMC between baseline and 6 months and between baseline and 12 months. The Institutional Review Board at Florida International University (FIU) approved the study. Also, a Data and Safety Monitoring Board (DSMB) was established and approved by NIH, with yearly meetings to assess safety reports.

Study population

Healthy children and adolescents aged 9-14 years were recruited in the Miami Metropolitan Area. Participants were recruited from various sources from X to X, as previously described (26). We aimed to recruit children and adolescents at a pubertal development (based on Tanner stage) of 2-4 to match the previous study on SCF supplementation for three-week in adolescents conducted by [name] (12). We also aimed to include only those children consuming 2 or fewer servings of dairy products per day, which translates into about 600 mg/d of calcium (half of the recommendation for this age group (27)) and consuming calcium supplements <200 mg/d. Participants were excluded if they had a body mass index (BMI) percentile above 95% for age and sex based on the Centers for Disease Control Growth Charts, any chronic illness requiring regular medication, or vitamin D deficiency (25OHD <20 ng/ml), as established by the Institute of Medicine for bone health (28). This criterion was assessed at the baseline visit. After finding many children with low vitamin D in the baseline visit (29), the protocol was amended to provide vitamin D supplements to those children for 6-8 weeks and once 25(OH)D was >20 ng/ml, they were randomized into the study.

Supplements

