Participants were randomized sequentially using a computer-generated block randomization list into four groups: SCF (12 g/d), SCF + calcium (12 g/d of SCF + 600 mg/d of elemental calcium), Placebo (12 g/d of maltodextrin); or Placebo + calcium (12 g/d of maltodextrin + 600 mg/d of elemental calcium). SCF and the maltodextrin were donated in part by Tate & Lyle PLC (Hoffman Estates, IL) and the calcium (in the form of calcium lactate gluconate) was purchased from Stauber

Fullerton, CA. Supplements were pre-mixed in our diet preparation lab at FIU by a dedicated research team not involved in the assessments and delivered to participants in large white canisters of the same size and weight with a color-coded lid for a 3-month supply. Participants were instructed to consume 1 scoop of product diluted in 8-10 ounces of liquid twice per day. The study supplements were tested several times per year for microbiology integrity (aerobic plate count, coliforms, E. coli, Salmonella, yeast, and mold) by an independent external laboratory.

To promote retention, participants were given the choice of either adding the supplement to their usual beverage (non-carbonated) or to be pre-mixed in our food lab with Kool-Aid (donated by Kraft). Several flavors were offered, and they could change the flavor every 3 months. We also provided a study water bottle to facilitate taking it to school, travel, or extracurricular activities. We also sent motivational text messages about the importance of taking the supplement, how to establish the habit of taking it daily, and ideas to vary the supplement using an automated one-way text message provider. The text messages were sent twice per week for the first 6 weeks and then the frequency was reduced to every 3 weeks until the end of the study. We provided enough supplement in each canister to share with family members.

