The main analyses will be performed on an intention-to-treat basis. Data was examined for outliers and normality. Descriptive statistics included means, medians, standard deviations, and ranges for continuous variables and frequencies and proportions for categorical variables. ANOVA and chi-square test were used to compare means and proportions by treatment group. We used the same analytical methods to examine potential differential attrition by treatment group. We compared characteristics and determined missing data mechanism between study completers and those with missing outcome data, using two-sample t-test for continuous and chi-square test for categorical variables. For the primary analysis, percent change from baseline in whole-body BMC after one year of supplement was compared between the two groups using analysis of covariance, adjusted for baseline age, sex, Tanner stage (puberty status), weight velocity and height velocity. Data was analyzed using SPSS. Effects were considered significant at the alpha level of 0.05.

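### The primary ANCOVA does not adjust for baseline BMC, adjusts for growth measured after randomisation with no version without it, and states no method for missing 12-month scans

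*Combined protocol and SAP*

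**What the plan says.** The Statistical plan section opens its analysis text with "The main analyses will be performed on an intention-to-treat basis" and gives one primary model: "percent change from baseline in whole-body BMC after one year of supplement was compared between the two groups using analysis of covariance". The covariate list of that model reads "adjusted for baseline age, sex, Tanner stage (puberty status), weight velocity and height velocity".

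Missing data appear there only as checks. One is "We used the same analytical methods to examine potential differential attrition by treatment group". The other compared characteristics and "determined missing data mechanism between study completers and those with missing outcome data, using two-sample t-test" for continuous variables, with chi-square tests for categorical ones. No imputation, likelihood-based method or sensitivity analysis is named. The sample-size paragraph allows for 20% drop-out.

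Under Measurements, weight, height and DXA are taken at baseline, 6 and 12 months. Each velocity is the change in weight or height divided by the age difference between successive annual visits. The Diet and Physical activity entries say that dietary intakes and physical activity serve as covariates, but the primary model does not list them.

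**The concern.** Three features of one model are at issue.

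- **Baseline BMC.** It is collected and is the denominator of the outcome, but it is not a covariate. If percent change depends on starting BMC, the model forgoes some precision and leaves chance imbalance in baseline BMC uncorrected.
- **Velocities.** The first annual interval in this trial runs from baseline to 12 months, so both velocities are measured after assignment, whatever the word baseline in the covariate list is meant to cover. Adjusting for them removes any part of the effect that acts through growth. Without a second version, a reader cannot see whether this matters.
- **Missing 12-month visits.** A child without that visit has no outcome and no annual velocity, so the model drops the child. The attrition and completer comparisons describe the loss but do not change the estimate. If reasons for leaving differ by arm while drop-out rates are equal, a comparison of rates by arm will not show it. The 6-month data could help, but the primary model does not use them.

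**Working it through.** From the plan: 40 per group, 0.5 SD, alpha 0.05 (taken as two-sided), 20% drop-out. Assumed, because the documents give no values: all correlations and drop-out mechanisms below. Effects are in SD of 12-month percent change, and the two velocities are treated as one covariate.

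**1. The plan's own figure.** Unadjusted SE = sqrt(2/40) = 0.2236. With 78 df the two-sample t test has 59.8% power, not the stated 80%. By the normal approximation 80% needs 2 x ((1.960 + 0.842)/0.5)^2 = 62.8 per group, so 40 suffices only if covariates explain 1 - 40/62.8 = 36% of the variance. The documents do not say so. This is a separate matter. It is used here only to show that results depend on the SE.

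**2. Adjusted SE.** If velocity correlates 0.3 with the outcome, SE = sqrt(0.05 x 0.91) = 0.213. If 0.6, SE = sqrt(0.05 x 0.64) = 0.179. A simulation at 0.6 (50 randomised per arm, 20% random loss, 1,500 runs) gave a mean SE of 0.175 for children with 12-month data.

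**3. Gain from baseline BMC.** Multiply the residual variance by 1 - r^2, where r is its partial correlation with the outcome.

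| Starting SE | Power now | r = 0.1 | r = 0.2 | r = 0.3 | r = 0.4 | Gain (points) |
|---|---|---|---|---|---|---|
| 0.2236 (unadjusted) | 59.8% | 60.2% | 61.6% | 63.9% | 67.4% | 0.4 to 7.5 |
| 0.179 | 78.8% | 79.2% | 80.4% | 82.4% | 85.3% | 0.4 to 6.5 |
| 0.175 | 80.5% | 80.9% | 82.1% | 84.1% | 86.8% | 0.4 to 6.3 |

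Charging one degree of freedom changes these by less than 0.1 point.

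**4. Bias from dropping children without a 12-month visit.** Simulation with 1,000,000 per arm and equal 20% loss: 10% random early loss plus 10% late loss, with late-loss log-odds of -0.5 to -1.5 per SD of the driving variable. The 6- and 12-month changes correlate 0.6. Baseline BMC correlates -0.2 with both. Velocity correlates 0.5/0.6 or 0.25/0.3 with the 6-/12-month changes.

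| Late loss | Bias, velocity-adjusted ANCOVA (SD) |
|---|---|
| Same pattern in both arms | -0.002 to 0.003 |
| Active arm only, tied to 6-month change | 0.016-0.041 (correlation 0.6); 0.028-0.072 (0.3) |
| Opposite patterns by arm | 0.032-0.084 (0.6); 0.056-0.142 (0.3) |
| Active arm only, tied to baseline BMC | -0.028 to -0.009; about 0 with baseline BMC added |

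A repeat with fresh code gave 0.015-0.042 and 0.032-0.069 for the second row. Imputation within arm from baseline and 6-month values left at most 0.003 SD. That follows from how missingness was simulated: it depended only on variables in the imputation model, or on nothing. Imputation brought no precision: mean SE 0.179 against 0.175, empirical SE 0.177 for both.

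**5. Tipping shift.** With 20% of the active arm imputed, a shift of d moves the estimate by 0.20 x d. For an observed 0.50 SD difference, significance is lost at d = (0.50 - t x SE)/0.20, with the SE held fixed.

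| SE | t x SE | p at 0.50 | Tipping shift | p after a -0.5 SD shift |
|---|---|---|---|---|
| 0.2236 | 0.445 | 0.028 | 0.27 SD | 0.078 |
| 0.213 | 0.425 | 0.022 | 0.38 SD | 0.065 |
| 0.179 | 0.357 | 0.007 | 0.72 SD | 0.028 |
| 0.175 | 0.349 | 0.006 | 0.76 SD | 0.025 |

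**6. Velocity adjustment, only if the supplement changes growth.** Adjusted effect = 0.50 - (correlation x effect on velocity). If the supplement raised velocity by 0.1 to 0.3 SD, the result would be 0.47 to 0.41 at correlation 0.3 and 0.44 to 0.32 at 0.6. If growth is unaffected, nothing is lost.

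**The case against.** The strongest defence is that the plan is not silent on missing data. It enlarges the sample for drop-out, tests for differential attrition and compares completers with the rest. Intention-to-treat can mean analysis by assigned arm, and then the label is not false. The trial is double-blinded, and nothing in the documents suggests that drop-out would follow bone change differently by arm. Adjusting bone accrual for growth is a defensible choice of what to estimate. Trial details are said to be published elsewhere, and that source is not available here.

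Much of this stands, and it rules out several stronger readings.

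- A reader might infer that the model ignores baseline BMC altogether. It does not: percent change uses it as the denominator. Only the covariate is absent.
- A reader might infer that the main estimate is biased. That needs drop-out to work differently by arm, which the documents do not show. The 0.14 SD extreme needs opposite patterns.
- A reader might infer fragility from the 0.27 SD tipping shift. That figure uses the unadjusted SE, which is not that of the planned ANCOVA.
- A reader might infer that velocity adjustment does shrink the effect. No passage says that the supplement alters growth.

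The defence leaves three gaps. The diagnostics lead to no action, and tests on observed characteristics cannot rule out data missing not at random. The plan never says which children are analysed. No version without the post-randomisation covariates is offered.

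**Conclusion.** The point holds at modest size. As written, the primary ANCOVA lacks baseline BMC as a covariate, conditions on two post-randomisation variables with no alternative version, and keeps only children with a 12-month visit. With every input assumed, bias is about 0 when the arms lose children alike and about 0.02 to 0.07 SD when only active-arm loss follows 6-month bone change. The upper end is about a third of an SE of 0.213. Baseline BMC brings a small to moderate power gain for one degree of freedom. Robustness to missing data depends strongly on how much the velocities explain: the tipping shift runs from 0.27 SD unadjusted to 0.76 SD. Imputation corrects bias only under missing at random and should not be presented as a gain in precision. The unanalysed 6-month and spine outcomes named under Study rationale and overall design are a separate issue.

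**What to change.** 1. Add baseline whole-body BMC to the ANCOVA. Cost: one degree of freedom.
2. Report the same ANCOVA without the two velocities, as a sensitivity result beside the main one. Cost: a wider interval.
3. Add one multiple-imputation sensitivity analysis of all randomised children with a baseline scan. Impute 12-month BMC, weight and height within assigned arm ("Participants were randomized sequentially using a computer-generated block randomization list into four groups") from baseline and 6-month values. Then shift the imputed values in the SCF-containing group of the tested contrast, continuing until the conclusion changes. A grid that stops at -0.5 SD may not reach that point. Cost: analysis time only; no new data.
4. Report the number analysed, and describe the ANCOVA set as children with a 12-month scan, analysed as randomised. State whether dietary intakes and physical activity enter this model.

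The document is dated 09/26/2025 and describes much of the analysis in the past tense. If the data are already unblinded, keep the original ANCOVA as the main result and label items 1 to 3 post hoc.

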Compliance was carefully monitored during the trial and recorded in different ways. We initially developed an app to record compliance daily, but after discussing with parents their use, this was changed to a weekly survey sent by text. We also provided a paper calendar as an alternative. We asked families to record the number of supplements consumed per day (2, 1, or 0). Parents received extra compensation for monitoring supplement intake every 3 months. In addition, they were asked to complete a short questionnaire about the study supplement intake at every visit (3, 6, 9 and 12 months). Lastly, we reviewed compliance at every visit verbally. There was a dedicated person compiling the various sources of compliance information to identify when data was missing and if we needed to contact parents to discuss low compliance.

Measurements

As previously described (25), the research team was blinded to the supplement type. Participants were asked to complete three visits (baseline, 6 months, and 12 months) at our FIU labs to undergo anthropometrics and a bone scan, and complete health questionnaires. Also, participants were asked to provide a fasting blood sample, a 24-h urine collection, and a fecal sample at baseline and

12 months. We also visited participants at their home or other convenient place for the 3- and 9-months visits to deliver more supplements and complete health questionnaires.

General health and socio-demographics: this included parental age, sex, education, and medical history and children's age, sex, self-reported pubertal maturity using Tanner staging (30) and menarche date (if applicable), fracture(s) history, use of medications, use of alcohol and tobacco, sleep and stress.

Anthropometric measurements: weight, height, and waist circumferences were assessed by trained study staff at baseline, 6-month and 12-month following standardized protocols. Weight velocity and height velocity were calculated as the difference in weight or height, divided by the difference in age between consecutive annual study visits. Height velocity <0 cm/year was assumed to reflect a measurement error after reaching adult height and was recoded to 0.

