Bone mass: Whole body and spine BMC and BMD were assessed using a Hologic dual-energy X-ray absorptiometry (DXA) scan at our FIU DXA Lab at baseline, 6-month and 12-month following standardized protocols. All scans were performed by trained personnel, with the Florida Department of Health Certification for Basic X-ray machine operator.

Blood sample: a fasting blood sample (15 ml each) was collected at baseline and 12-months by venipuncture by research trained phlebotomists. Samples were immediately centrifuged; part was sent to a commercial lab for 25(OH)D, calcium, phosphorus, and creatinine. The rest was stored at -80°C for future analyses.

Urine sample: a 24-h urine sample was collected at baseline and 12-months and analyzed by a commercial lab for calcium, phosphorus, and creatinine.

Diet: Three 24-h recalls were collected at baseline, and a 24-h recall was collected at 3, 6, 9, and 12 months. Dietary recalls were analyzed using the Nutrition Data System for Research (NDSR) software. Total energy intake and intakes of protein, calcium, vitamin D were calculated to be used as covariates in the statistical analyses.

Physical activity: This was collected at each visit using the International Physical Activity Questionnaire (IPAQ) (31) and used as a covariate in the statistical analyses.

Gastrointestinal symptoms: This was recorded every 3 months with a survey asking participants for abdominal pain, bloating, flatulence or diarrhea.

Statistical plan

Sample size was calculated for the primary outcome (change in whole-body BMC over 1 year between SFC and control) based on a conservative clinically meaningful standardized effect size (32), as when the study started, there were no previous studies assessing the effects of SCF on bone. For an alpha level of 0.05, 40 in each group provides 80% power to detect a medium effect size of 0.5 units of standard deviation (33) in BMC between any of the active treatment groups compared to placebo. This was inflated by >30% for non-eligible rate due to vitamin D deficiency (10%) plus drop-out rate similar to rates in our previous trials among adolescents (20%) (34–38). All power calculations were performed with PASS2019 (39).

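### The primary ANCOVA of percent change in whole-body BMC leaves out baseline BMC; adding it is cheap, but the gain is unknown and may be nil

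*Combined protocol and SAP*

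**What the plan says.** The Statistical plan defines the primary analysis in one sentence. Its outcome and method are given as "percent change from baseline in whole-body BMC after one year of supplement was compared between the two groups using analysis of covariance". The rest of that sentence lists the covariates, and the model is to be "adjusted for baseline age, sex, Tanner stage (puberty status), weight velocity and height velocity". Two paragraphs under Measurements name further covariates. The Diet paragraph covers total energy and says that "intakes of protein, calcium, vitamin D were calculated to be used as covariates in the statistical analyses"; the Physical activity paragraph says that the questionnaire result is "used as a covariate in the statistical analyses". Baseline BMC appears in none of these places.

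The value exists for every child who can be analysed. The Bone mass paragraph says that whole-body and spine scans were done "at our FIU DXA Lab at baseline, 6-month and 12-month following standardized protocols".

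Two other statements bear on the point. The Anthropometric measurements paragraph defines the velocities as "the difference in weight or height, divided by the difference in age between consecutive annual study visits", so they are measured after randomisation. On timing, the Statistical plan ends with "Data was analyzed using SPSS", in a document dated 09/26/2025.

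**The concern.** A percentage change is free of its baseline only if the expected gain is proportional to the starting value, and the plan does not claim this. If children with higher baseline BMC tend to have systematically larger or smaller percent changes after allowing for age, sex, Tanner stage and the velocities, that relation is left in the error term. The confidence interval is then wider than it needs to be.

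Age, sex and Tanner stage correct part of any chance difference between arms in baseline BMC. The part they do not explain carries into the estimate. That is the same loss of precision seen within a single trial, not a second harm. With respect to baseline BMC, the omission causes no bias on average over randomisation. That statement does not extend to the two velocities, which raise a separate question.

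**Working it through.** **Inputs.** From the Statistical plan: the covariate list, alpha 0.05 (two-sided assumed), 40 per group and an effect of 0.5 SD. The documents give no SD, no correlation of baseline BMC with percent change and no R² for the covariates. Two quantities are therefore assumed: r, the partial correlation of percent change with baseline BMC given the planned covariates (0 to 0.5), and R², the share of baseline BMC that those covariates explain (0, 0.5, 0.7).

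**The plan's own figure.** It states that "40 in each group provides 80% power to detect a medium effect size of 0.5 units of standard deviation". For two arms of 40, power = Φ(0.5/√(2/40) − 1.96) = Φ(2.236 − 1.96) = 60.9%, and 80% needs 63 per group. The stated 80% does not reproduce for that comparison. That is a separate matter and nothing below depends on it. The power figures here only illustrate the effect of one covariate.

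**Residual variance.** Adding baseline BMC multiplies residual variance by 1 − r². For |r| = 0, 0.2, 0.3, 0.4, 0.5 the reduction is 0%, 4%, 9%, 16%, 25%.

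**Power by formula, 40 per arm, no charge for covariates.** Φ(0.5/√((1 − r²) × 2/40) − 1.96), with 0.5 in residual SD of the planned model, gives 60.9%, 62.6%, 65.0%, 68.4%, 73.3%. If 0.5 is in raw SD and the planned covariates explain 30% of the variance of percent change (assumed), the effect is 0.5/√0.7 = 0.598 residual SD, and the series is 76.2%, 77.9%, 80.0%, 83.0%, 87.0%.

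**Power by simulation.** Both models contain age, sex, Tanner stage 2–4 as two dummies, and the two velocities (6 df); the second adds baseline BMC. There were 10,000 trials per setting, averaged over the three R² values. The velocities were simulated as unaffected by treatment, and the diet and activity covariates were not simulated. Average type I error was 4.7% to 5.2% in both models.

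| \|r\| | Planned, 40 per arm | With baseline BMC | Change (points) | SE ratio | Planned, 80 per group | With baseline BMC |
|---|---|---|---|---|---|---|
| 0 | 56.6% | 55.8% | -0.7 | 1.007 | 86.8% | 86.6% |
| 0.2 | 56.9% | 57.9% | +0.9 | 0.987 | 87.2% | 88.2% |
| 0.3 | 56.1% | 59.6% | +3.5 | 0.961 | 86.8% | 89.4% |
| 0.4 | 56.2% | 62.9% | +6.8 | 0.923 | 86.7% | 91.9% |
| 0.5 | 57.0% | 68.4% | +11.4 | 0.873 | 86.7% | 94.3% |

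Changes come from unrounded values and can differ by 0.1 from the displayed columns. The 80-per-group columns apply if the two groups in the primary analysis are pooled arms, which the plan does not say.

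**Break-even.** Going from 6 to 7 covariate df inflates the variance of the treatment estimate by (N − 9)/(N − 10), through chance covariate imbalance. The added term pays when r² > 1/(N − 9). N = 80 gives |r| > √(1/71) = 0.119; N = 160 gives |r| > √(1/151) = 0.081.

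**Chance imbalance within one trial, 40 per arm.** If the arms differ by 0.2 SD in baseline BMC, the planned estimate shifts on average by |r| × 0.2 × √(1 − R²) residual SD; one SE is √(2/40) = 0.224 SD.

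- |r| = 0.5: 0.10 SD (0.45 SE) at R² = 0; 0.07 SD (0.32 SE) at R² = 0.5; 0.055 SD (0.25 SE) at R² = 0.7.
- |r| = 0.2, R² = 0.5: 0.03 SD (0.13 SE).

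A total imbalance of 0.2 SD or more occurs in about 37% of randomisations, whatever R² is. A different event, an imbalance of that raw size in the unexplained part alone, has probability 37%, 21% and 10% for R² = 0, 0.5 and 0.7. The last two probabilities should not be paired with the shifts above.

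**The case against.** The strongest reply is that no harm has been shown. The outcome is already scaled by baseline, and age, sex, Tanner stage and the velocities may carry most of what baseline BMC would add. Below |r| of about 0.12 the extra term costs a little, and at 0.2 it gains about one point. Holding r fixed while R² varies also flatters the upper rows. With a fixed slope b on baseline BMC and a fixed remaining error SD of 1, r² = b²(1 − R²)/(b²(1 − R²) + 1). With b² = 1/3, r is 0.50 at R² = 0, 0.38 at R² = 0.5 and 0.30 at R² = 0.7, so the +11.4 points would become about +3.5 at R² = 0.7. Further, the five diet and activity covariates were not simulated, fuller details are said to be published elsewhere, and the analysis appears to be finished.

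Most of this stands as a limit on size. The upper rows need a strong relation that survives the planned adjustment, and nothing in the documents shows one. It does not remove the point. The covariate sentence is complete and omits the variable, r is defined as what remains after the planned covariates, and Tanner stage is self-reported and so an imperfect marker of maturity. The worst case is under one power point at 40 per arm. The timing changes the remedy, not the observation.

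**Conclusion.** The point holds as a low-cost efficiency improvement, not as an error that invalidates the analysis. Baseline BMC is missing from every covariate list in the document although it is measured and needed for the outcome itself. The gain cannot be determined from the documents. At 40 per arm it runs from a loss of about 0.7 power points if r = 0, through a gain of about 3.5 at |r| = 0.3, to about 11 at |r| = 0.5; with 80 per group the gain at 0.5 is 7.6 points. These figures rest on assumed r and R², on reading 0.5 as an effect in residual SD of the planned model, and on a model without the diet and activity terms. Confidence that baseline BMC is omitted is high; confidence that the gain is material is only moderate.

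**What to change.** If the data are not yet unblinded, add baseline whole-body BMC to the stated ANCOVA and leave its other covariates unchanged. Add baseline spine BMC to the corresponding spine analysis; Study rationale and overall design names spine BMC in the primary outcome, but the Statistical plan describes no spine model.

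If the data are already unblinded, as the past tense and the date suggest, keep the planned model as primary and report the baseline-adjusted model beside it as a labelled sensitivity analysis. Reporting the partial correlation as well would show whether the omission mattered.

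The cost is one degree of freedom and one extra model per outcome, with no new data and no further loss of participants. If r = 0 there is no gain, and a loss of about half to three quarters of a power point at 40 per arm. Whether to keep the post-randomisation velocities should be decided separately; r here is defined with them in the model and would differ without them.
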